# 6.6 Participation in an Open-label Extension Study

An open-label extension study at the recommended Phase 3 dose and regimen (as derived from Study ALN-TTR02-002) is planned, which will enable the patients who enrolled in Study ALN-TTR02-002 to receive additional, long-term dosing and safety follow-up. For some of the patients, this may preclude the completion of all of the follow-up period assessments of Study ALN-TTR02-002 if they are deemed eligible to participate in the extension study prior to completion of the full follow up through Day 208. Such patients will be followed up for a minimum of 28 days after their last dose in the current ALN-TTR02-002 study prior to being enrolled in the extension study. The extension study will be implemented only after dose escalation is completed in Study ALN-TTR02-002, with post second dose follow-up through Day 208 in at least 1 cohort at the highest dose deemed safe.

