The area under the concentration-time curve (AUC) will be calculated for serum TTR. The AUC will be calculated using the daily TTR concentrations starting from baseline, defined as the average of all pre-dose values, and continuing to the Day 28 premedication assessment (Day 21 for optional cohorts dosed every 3 weeks). The trapezoidal rule will be used for the calculation of AUC. For the purpose of this AUC calculation, it is assumed that the collection times are in multiples of equal 24 hour intervals. For example, the interval from Day 2 to Day 4 will be 48 hours, irrespective of actual assessment times. AUC will be summarized using descriptive statistics. A similar calculation and summary will be performed for the AUC calculated from Day 28 to Day 56 (Day 21 to Day 42 for optional cohorts dosed every 3 weeks).

TTR levels over time will be plotted. Each subject's TTR levels will be joined by a line, and each subject within a dose group will have a different symbol. A separate plot will be produced for each dose group. In addition, the average of each dose group (with standard error bars) will be plotted versus time. Dose group means (with standard error bars) for percent change from baseline will be plotted over time.

The pharmacodynamics assessment for use in the PK/PD analysis will be similar to that described above, but may include additional PD analyses which will be used for the purpose of PK/PD analysis. The methods for the PK/PD analysis will be described in the PK and PK/PD analysis plans and the analysis result will be reported in the separate PK and PK/PD report which will be appended to the CSR.

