7.3. Figures to be Generated

Figure 14.2.1.1	Individual TTR (ELISA) Levels over Time
Figure 14.2.1.2	Individual Wild Type TTR (LCMS/MS) Levels over Time
Figure 14.2.1.3	Individual Mutant TTR (LCMS/MS) Levels over Time
Figure 14.2.2.1	Mean TTR (ELISA) Levels by Dose Group over Time
Figure 14.2.2.2	Mean Wild Type TTR (LCMS/MS) Levels by Dose Group over Time
Figure 14.2.2.3	Mean Mutant TTR (LCMS/MS) Levels by Dose Group over Time
Figure 14.2.3.1	Mean Percent Change from Baseline in TTR (ELISA) by Dose Group over Time
Figure 14.2.3.2	Mean Percent Change from Baseline in Wild Type TTR (LCMS/MS) by Dose Group over Time
Figure 14.2.3.3	Mean Percent Change from Baseline in Mutant TTR (LCMS/MS) by Dose Group over Time
Figure 14.2.4.1.1	TTR (ELISA) at Individual Nadir by Dose Group
Figure 14.2.4.1.2	Mean Percent Change from Baseline in TTR (ELISA) at Individual Nadir by Dose Group
Figure 14.2.4.2.1	Wild Type TTR (LCMS/MS) at Individual Nadir by Dose Group
Figure 14.2.4.2.2	Mean Percent Change from Baseline in Wild Type TTR (LCMS/MS) at Individual Nadir by Dose Group
Figure 14.2.4.3.1	Mutant TTR (LCMS/MS) at Individual Nadir by Dose Group
Figure 14.2.4.3.2	Mean Percent Change from Baseline in Mutant TTR (LCMS/MS) at Individual Nadir by Dose Group
Figure 14.2.5.1	Mean Percent Change from Baseline in TTR (ELISA) at Group Nadir by Dose Group
Figure 14.2.5.2	Mean Percent Change from Baseline in Wild Type TTR (LCMS/MS) at Group Nadir by Dose Group
Figure 14.2.5.3	Mean Percent Change from Baseline in Mutant TTR (LCMS/MS) at Group Nadir by Dose Group
Figure 14.2.6	Mean Percent Change from Baseline in TTR (ELISA) at Individual Nadir by Dose Group and Stabilizer Use – 300 µg/kg Subjects
Figure 14.2.7.1	Area under the TTR (ELISA) Concentration-Time Curve
Figure 14.2.7.2	Area under the Wild Type TTR (LCMS/MS) Concentration-Time Curve
Figure 14.2.7.3	Area under the Mutant TTR (LCMS/MS) Concentration-Time Curve
Figure 14.2.8	Individual Vitamin A Levels over Time
Figure 14.2.9	Mean Vitamin A Levels by Dose Group over Time

Figure 14.2.10	Mean Percent Change from Baseline in Vitamin A by Dose Group over Time
Figure 14.2.11	Mean Percent Change from Baseline in Vitamin A at Individual Nadir by Dose Group over Time
Figure 14.2.12	Mean Percent Change from Baseline in Vitamin A at Group Nadir by Dose Group over Time
Figure 14.2.13	Individual Relative Retinol Binding Protein Levels over Time
Figure 14.2.14	Mean Retinol Binding Protein Levels by Dose Group over Time

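### Raw serum TTR AUC spans 28 days in the 4-week cohorts but 21 days in the 3-week cohorts, so at the same mean TTR the 3-week value is 25% lower

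*SAP*

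**What the plan says.** SAP 4.3.1 defines an area under the serum TTR concentration-time curve for each subject. For the first dose the starting value is the mean of the measurements taken before dosing. The end of the window depends on the regimen: "continuing to the Day 28 premedication assessment (Day 21 for optional cohorts dosed every 3 weeks". For the second dose a similar calculation is made of "the AUC calculated from Day 28 to Day 56 (Day 21 to Day 42 for optional cohorts dosed every 3 weeks". On method: "The trapezoidal rule will be used for the calculation of AUC". Time is nominal; in the SAP's own example, "the interval from Day 2 to Day 4 will be 48 hours, irrespective of actual assessment times". The result goes straight into descriptive statistics. Neither document mentions division by the length of the interval, a percent-of-baseline AUC or a window common to both regimens.

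SAP 3.5 tabulates the 4-week and 3-week groups separately, and the AUC tables follow that rule (14.2.4.1A/B to 14.2.4.3A/B). The AUC figures, 14.2.7.1 to 14.2.7.3, have titles such as "Area under the TTR (ELISA) Concentration-Time Curve", with no regimen named. SAP 3.2 plans no hypothesis tests.

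On the use of the results, Protocol 6.6 says: "An open-label extension study at the recommended Phase 3 dose and regimen (as derived from Study ALN-TTR02-002) is planned".

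**The concern.** A concentration-time total grows with the length of the window. The two regimens have windows of different length, so their totals are on different scales. Since less TTR means more suppression, the shorter window makes the 3-week regimen look better for a reason unrelated to the drug.

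The first interval shows this most clearly. By its end each patient has had exactly one dose, so at equal dose and premedication the two regimens have not yet diverged. Any 3-week versus 4-week difference in raw AUC that comes from the window alone is then pure artefact.

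AUC is also the only summary in SAP 4.3.1 that integrates TTR over a whole dosing interval, and the only listed PD output that scales with window length. Concentrations, percent changes and nadirs do not. The optional cohorts exist partly to evaluate 3-weekly dosing (Protocol 5.7.2), so readers can be expected to look across regimens.

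Two smaller weaknesses sit in the same definition. Without baseline scaling, differences in starting TTR enter the group means. Cohorts have 3 patients (Protocol 4.4.1), and eligibility sets no TTR limit (Protocol 4.2 and 4.3). Nominal timing also ignores visit dates that are available.

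**Working it through.** The plan states no AUC value, so there is no figure to reproduce. Its timing example checks: Day 2 to Day 4 is 2 × 24 = 48 hours.

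**Inputs.** Windows are from SAP 4.3.1: 28 days (672 h) and 21 days (504 h), for each dose. TTR sampling days are from Protocol 7.3.1: 0, 1, 2, 7, 10, 14, 21 and, for 4-week cohorts, 28. The TTR time course is not given, so the profiles below are assumptions.

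**Equal mean level.** Raw AUC = mean level × days. With the same mean *m*, the ratio is 21*m* / 28*m* = 0.75, so the 3-week AUC is 25% lower. This holds in both intervals.

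**Identical first-dose curve.** Let *m*₁ be the mean over Days 0-21 and *m*₂ the mean over Days 21-28. The ratio is 21*m*₁ / (21*m*₁ + 7*m*₂). TTR is positive, so the ratio is always below 1. It equals 0.75 only if *m*₁ = *m*₂. The gap exceeds 25% if TTR in the fourth week is above the earlier mean, and is smaller if it is below.

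**One profile in full** (percent of baseline: Day 0 100, Day 1 70, Day 2 50, Day 7 20, Day 10 17, Day 14 20, Day 21 30, Day 28 45):

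- Days 0-21: 85 + 60 + 175 + 55.5 + 74 + 175 = 624.5 %-days
- Days 21-28: 7 × (30 + 45)/2 = 262.5, so Days 0-28 = 887
- Ratio 624.5/887 = 0.704, about 30% lower
- Per day: 624.5/21 = 29.7 and 887/28 = 31.7

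**Range over assumed shapes, first interval** (AUC in %-days, trapezoids at the nominal days):

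| Assumed profile | AUC 0-21 | AUC 0-28 | Raw difference | Per-day means (3-week, 4-week) | Difference after dividing |
|---|---|---|---|---|---|
| Falls to 20 by Day 7, held | 675 | 815 | −17.2% | 32.1, 29.1 | +10.4% |
| Falls to 50 by Day 7, held | 1226 | 1576 | −22.2% | 58.4, 56.3 | +3.7% |
| 59 at Day 7, rising to 80 at Day 28 | 1480.5 | 2016 | −26.6% | 70.5, 72.0 | −2.1% |
| Nadir 20 at Day 10, then 50 and 80 at Days 21 and 28 | 840 | 1295 | −35.1% | 40.0, 46.2 | −13.5% |
| Nadir 15 at Day 10, then 60 and 100 at Days 21 and 28 | 794.5 | 1354.5 | −41.3% | 37.8, 48.4 | −21.8% |

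Dividing by length therefore removes the gap completely only at a constant level. A common Day 0-21 window gives exactly 0% for identical first-dose curves, whatever their shape.

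**Second interval.** Assume each regimen starts from its own trough and reaches the same levels after dosing. The raw difference is then −25.0% if suppression is sustained, and about −29% to −44% for the recovering profiles. Part of the latter is real, because the 3-week patient is re-dosed from a lower level. The raw total cannot separate the two parts.

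**Nominal timing** (windows from Protocol Tables 1-1 and 12-1). In 4-week cohorts Day 14 ± 3 is Day 11-17 and Day 21 ± 3 is Day 18-24. The gap is 18 − 17 = 1 to 24 − 11 = 13 days. In 3-week cohorts the second dosing visit is Day 21-23, so the gap is 21 − 17 = 4 to 23 − 11 = 12 days. Both count as 7.

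**The case against.** The best defence is that the plan never sets the regimens against each other on AUC. The tables are split, SAP 3.2 rules out testing and formal conclusions, and comparisons of dose levels within a regimen all use the same window. This stands, and it confines the artefact to readings across regimens.

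The figure titles are weak evidence of pooling. No figure in the SAP list has a regimen split, whatever its endpoint, and SAP 4.3.1 does not describe the layout of the AUC figures. A reader might infer that both regimens will share an axis. The documents leave that open, and it matters only if they do.

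AUC also has company. Section 4.3.1 reports nadirs, percent reduction at the end of each dosing interval, and percent change with confidence intervals at each time point. None of these depends on window length in the same way. No text says that the Phase 3 regimen will be chosen on AUC, and the PK/PD work is in a separate plan that was not supplied. So a reader may not conclude that this AUC will decide the regimen.

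Finally, nominal visits are the SAP's general convention (3.11), and no direction of bias between regimens follows from them. That is fair: actual dates improve accuracy here but are not part of the 25%.

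These points limit the harm but do not make the two totals comparable. Splitting the tables without saying that the windows differ still leaves adjacent outputs with one name and two scales.

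**Conclusion.** The point holds as a defect of definition. Raw TTR AUC has a regimen-dependent window and no normalisation, so at equal mean TTR the 3-week value is exactly 25% lower in both intervals. For identical first-dose curves it is always lower. The 17% to 41% range depends on assumed shapes and is not a bound; no single figure other than the 25% at equal mean follows from the documents.

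A tempting stronger reading is that the definition favours the 3-week regimen whatever the drug does. It does not: if mean TTR under 3-weekly dosing were more than 28/21 = 4/3 of the 4-weekly mean, its raw AUC would be the higher one.

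The point matters only if 3-week cohorts are run, since they are optional, and only for comparisons across regimens. The missing baseline scaling applies within a regimen too. It is worth correcting because the study is meant to inform the regimen and the remedy uses data already collected.

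**What to change.** In SAP 4.3.1, Tables 14.2.4.x and Figures 14.2.7.x, for ELISA, wild-type and mutant TTR:

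- For each dosing interval, report time-averaged TTR: trapezoidal AUC on actual sample dates, divided by the interval length in days, as a percentage of the subject's baseline.
- For the first dose, also report a Day 0-21 AUC for all cohorts on the same percent-of-baseline scale, interpolating linearly to Day 21 where the sample falls on another day. This is needed because dividing by length does not equalise curves that are not flat.
- Keep raw AUC in the listings, with a note that it is not comparable across regimens.

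The cost is SAP wording, a small amount of extra programming and one additional summary. No new samples or visits are needed.

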4.3.2. Vitamin A and Retinol Binding Protein

Observed values and changes from baseline in vitamin A through Day 208 will be summarized for each scheduled time point using descriptive statistics. Percent change from baseline will also be summarized. Ninety-five percent CIs for percent change will be presented.

Vitamin A levels over time will be plotted. Each subject's vitamin A levels will be joined by a line, and each subject within a dose group will have a different symbol. A separate plot will be produced for each dose group. In addition, the average of each dose group (with standard error bars) will be plotted versus time. Dose group means (with standard error bars) for percent change from baseline will be plotted over time. Percent reduction from baseline at individual and group nadirs will be plotted as described above for serum TTR.

The above summaries will also be performed for RBP.

A scatter plot of total serum TTR protein versus vitamin A and RBP, all normalized to their respective baseline values, will be produced. The plot will include Spearman's correlation coefficients (ρ) and the p-values from the tests of $\rho = \text{zero}$, to assess the strength of the correlations between serum TTR and vitamin A and between serum TTR and RBP.

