### 7.3.2.1 Vitamin A and Retinol Binding Protein

Blood for measurements of vitamin A and RBP is to be collected at Screening, immediately prior (within 10 minutes) to the administration of the premedications, immediately pre-dose (within 10 minutes) on Days 0 and 28, and on Days 1, 2, 7, 10, 14, 21, 29, 30, 35, 38, 42, 49, 56 (end-of-study), 112, and 208 or at the time of early termination. For optional cohorts dosed once every 3 weeks, blood for measurements of vitamin A and RBP will be collected at Screening, immediately prior (within 10 minutes) to the administration of the premedications, immediately pre-dose (within 10 minutes) on Days 0 (Baseline) and 21, and on Days 1, 2, 7, 10, 14, 22, 23, 28, 31, 35, 42, 49, 56 (end-of-study), 112, and 208 or at the time of early termination.

Serum samples will be evaluated by HPLC to determine vitamin A levels and by nephelometry to determine RBP levels.

The laboratory for serum vitamin A and RBP analysis is:

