3. GENERAL STATISTICAL METHODS

3.1. Sample Size Justification

Based on the planned dose escalation scheme, up to 27 patients are expected to be enrolled. Three patients are to be enrolled at each of 4 planned dose levels. An additional 5 cohorts of 3 patients may be enrolled onto 1 or more of these specified dose levels to further evaluate safety and tolerability or PD effects. The sample size was chosen based on previous experience in Phase 2 studies and was not based on power calculations.

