3.2. General Methods

All data listings that contain an evaluation date will contain a relative study day. Pre-treatment and on-treatment study days are numbered relative to the day of study medication dosing, which is designated as Day 0. For example, the day prior to study medication will be Day -1 and the day after study medication will be Day 1.

All output will be incorporated into Microsoft Word or Excel files, or Adobe Acrobat PDF files, sorted and labeled according to the International Conference on Harmonisation (ICH) recommendations, and formatted to the appropriate page size(s).

Tabulations will be produced for appropriate demographic, baseline, efficacy, and safety parameters. For categorical variables, summary tabulations of the number and percentage of subjects within each category (with a category for missing data) of the parameter will be presented. For continuous variables, the number of subjects, mean, median, standard deviation (SD), minimum, and maximum values will be presented.

All data will be presented in by-subject data listings.

As this is a Phase 2 dose-escalation trial, formal statistical hypothesis testing will not be performed. Although exploratory confidence intervals (CIs) will be presented as described below, no formal statistical conclusions will be made based on these estimates.

Subjects will be analyzed in the cohort to which they were originally assigned. Data will be tabulated for each dose group (i.e., dose level, regimen, and pre-medication regimen).

Laboratory data collected and recorded as below the limit of detection will be set equal to the lower limit of detection for the calculation of summary statistics.

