3.4. Baseline Definitions

Unless noted otherwise, baseline will be defined as the Day 0 pre-dose value when non-missing, otherwise the latest value from amongst any screening values will be used (i.e., the measurement closest to and prior to dosing will be considered baseline). For PD parameters (TTR, RBP, Vitamin A), baseline will be defined as the average of all pre-dose values (i.e., Screening and Day 0 pre-dose values).

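### SAP 4.3.2 attaches ordinary Spearman p-values to what reads as pooled serial data; if so, they treat repeated values from one patient as independent and are too small

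*SAP*

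**What the plan says.** The SAP text on the plot reads: "A scatter plot of total serum TTR protein versus vitamin A and RBP, all normalized to their respective baseline values, will be produced". The plot is to show Spearman coefficients "and the p-values from the tests of" rho equal to zero, and the stated purpose is "to assess the strength of the correlations between serum TTR and vitamin A and between serum TTR and RBP". There are two tests, TTR with vitamin A and TTR with RBP. The section does not say whether all visits, one value per patient or separate dose groups are meant. The figure list in SAP 7.3 contains no scatter plot that would settle it.

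On sampling, Protocol 7.3.2.1 schedules vitamin A and RBP on "Days 1, 2, 7, 10, 14, 21, 29, 30, 35, 38, 42, 49, 56 (end-of-study), 112, and 208", plus the draws before the second dose. Protocol 7.3.1 gives the same days for TTR. On normalisation, SAP 3.4 says: "For PD parameters (TTR, RBP, Vitamin A), baseline will be defined as the average of all pre-dose values".

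On inference, SAP 3.2 says "formal statistical hypothesis testing will not be performed" and then makes room only for exploratory confidence intervals. Protocol 9.2.6 allows exploratory statistical comparisons of PD data alongside description.

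**The concern.** The usual Spearman p-value is valid when the plotted pairs are independent. Serial values from one patient are not, for two reasons. Patients are likely to differ persistently in their levels, and every value of a marker in a patient is divided by the same baseline, so error in that baseline carries into all of that patient's points. If the serial points are pooled, the test credits the data with more information than they contain.

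Pooling is the plain reading. Section 4.3.2 deals with values through Day 208, and where the SAP wants one number per patient it says so, as with the individual nadir and the TTR AUC in 4.3.1. The scatter-plot sentence makes no such reduction.

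At stake is a statement of precision in the study report that the design cannot support. There is also a gap in consistency: 3.2 mentions only exploratory intervals, while 4.3.2 adds test p-values without calling them exploratory.

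**Working it through.** **Inputs from the documents**

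- Patients: SAP 3.1 has "Three patients are to be enrolled at each of 4 planned dose levels. An additional 5 cohorts of 3 patients may be enrolled", so 4 × 3 + 5 × 3 = 27. This reproduces the SAP's own maximum of 27.
- Times per patient: the 15 listed days plus the pre-second-dose time on Day 28, counted once, give m = 16. The three-weekly schedule also gives 16.
- Maximum number of pairs: 27 × 16 = 432.
- Baseline: three scheduled pre-dose values (Screening, Day 0 before premedication, Day 0 before dosing).

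**Assumptions, because the documents are silent**

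- Two-sided 5% level. The SAP sets no alpha.
- All serial points pooled.
- Equal ICC in both markers, varied over a range.
- No true association.

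**Closed form.** Under no association, the variance of the pooled correlation is inflated by about D = 1 + (m − 1) × ICC², and the false-positive rate is 2 × [1 − Φ(1.96/√D)].

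- ICC 0.2: D = 1 + 15 × 0.04 = 1.60; 1.96/1.265 = 1.549; rate 12.1%.
- ICC 0.5: D = 1 + 15 × 0.25 = 4.75; 1.96/2.179 = 0.899; rate 36.8%.

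**Simulation.** Two independent random-intercept series, 27 patients × 16 times, ordinary Spearman p-value, 4,000 runs per setting:

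| ICC | D | Closed form | Simulated | 432/D |
|---|---|---|---|---|
| 0 | 1.00 | 5.0% | 5.8% | 432 |
| 0.1 | 1.15 | 6.8% | 6.5% | 376 |
| 0.2 | 1.60 | 12.1% | 12.0% | 270 |
| 0.5 | 4.75 | 36.8% | 35.2% | 91 |
| 0.7 | 8.35 | 49.8% | 48.0% | 52 |

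The last column is the number of independent pairs that the 432 are worth. Simulation error is about 0.35 percentage points near 5% (√(0.05 × 0.95/4,000)), so the small excess at ICC 0.1 should not be over-read. D does not depend on the number of patients: with 12 patients the simulated rate at ICC 0.5 is also 35%.

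**Shared baseline alone.** Suppose the only noise is independent and of equal size at every draw. Dividing by a three-sample mean then induces a correlation of about (1/3)/(1 + 1/3) = 0.25 between a patient's points. D = 1 + 15 × 0.0625 = 1.94, and the closed form gives 15.9%. Simulating the division directly gives 15.1% with a CV of 0.1 and 15.4% with a CV of 0.2.

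**Decaying correlation.** With AR(1) correlation over the actual four-weekly visit days, and per-day correlation 0.5, 0.7, 0.9 and 0.95, the rates are 5.1%, 7.5%, 19% and 29% (2,000 runs each).

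**Alternatives.** One value per patient (the minimum, standing for the nadir; n = 27; ICC 0.1 to 0.7) gives 4.8% to 5.3%. Pooled rho with a test that permutes whole patients gives 4.7% at ICC 0.5 (600 runs).

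**The case against.** The best defence is that the unit of analysis is an inference from silence. Section 4.3.2 has just called for percent reduction at individual nadirs, so one point per patient is a possible reading, and on it the p-value is sound. This stands as a condition on the finding. It does not remove the need to act, because the text does not say so and the figure list does not help.

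A reader might infer that the p-values contradict a ban on testing. The documents do not support that. SAP 3.2 rules out formal testing, Protocol 9.2.6 permits exploratory comparisons, and SAP 3.7 describes a descriptive interpretation. What remains is an unlabelled p-value that fits 3.2 poorly.

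A reader might also infer that the error rate is bound to be far above 5%. That needs an ICC the documents do not give. The excess is small at ICC 0.1 or with fast-decaying correlation, and absent at zero.

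Nor is the p-value the SAP's only gauge of strength, since rho is named first. Finally, vitamin A and RBP are exploratory PD measures under SAP 1.2.5.1. Protocol 1.1.1 already describes RBP clearance as greatly reduced by binding to TTR, so no association is hardly a credible null and a false positive against it has little practical meaning. That limits the consequence. It also means the p-value answers no useful question.

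**Conclusion.** The point holds as an error in the analysis as written, on the plain reading that all serial values are plotted. The ordinary p-value is then too small whenever both markers are positively correlated within patients. Its size depends on a correlation that has to be assumed: from about 6.5% at ICC 0.1 to 48% at ICC 0.7, 5% to 29% under AR(1) decay, and about 15% from the shared baseline alone, against a nominal 5%. If one pair per patient is intended, there is no inflation and only the wording is at fault.

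The sample size "was not based on power calculations", no alpha is attached to these tests, and no dose, stopping or study conclusion rests on them. The correction is worth making because it replaces an unsupported statement of precision with a valid one from data already collected.

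**What to change.** In SAP 4.3.2, state which visits and dose groups enter the plot, and add the figure to the list in 7.3. Drop the p-values. Then report one of the following:

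- pooled rho with a 95% CI from a bootstrap that resamples whole patients, which keeps the co-movement over time that the plot may be meant to show; or
- rho across all dose groups on one value per patient, for example percent change at the individual nadir in a named dosing interval. The SAP already derives this for all three markers. AUC would need new derivations, because 4.3.1 defines it only for TTR.

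Either choice fits the allowance for exploratory intervals in 3.2. If the sponsor wishes to keep a p-value, it should come from one pair per patient or from permuting whole patients, and be labelled descriptive. The cost is a few lines of SAP text and a little programming, with no new data. The downside is a wider interval.
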